### 3.2. Benefit/Risk Assessment

#### 3.2.1. Risk Assessment

Based on the experience with osivelotor at the time of this Protocol Amendment, no participant has experienced any adverse reaction of clinical significance. The theoretical potential risk for osivelotor is decreased oxygen delivery, however there are no current adverse events attributed to the study drug that support this theoretical risk.

Potential Risk of Clinical Significance	Summary of Data/Rationale for Risk	Mitigation Strategy
Study Intervention Osivelotor (PF-07940367 or GBT021601)		
Decreased oxygen delivery	Increased oxygen affinity associated with the osivelotor mechanism has a theoretical potential to result in decreased oxygen delivery	Close monitoring of AEs through TME monitoring, vital signs, EPO levels, and hemoximetry Planned near infrared spectroscopy (NIRS) study to assess evidence of organ preservation designed to address this risk.
Study Procedures		

Potential Risk of Clinical Significance	Summary of Data/Rationale for Risk	Mitigation Strategy
Worsening anemia in participant with underlying sickle cell anemia.	Frequent blood samples will be collected from anemic participants during the study which may result in potential loss of blood volume in already anemic participants	A reduced PK sampling scheme is incorporated for pediatric participants so as not to exceed blood draw limits (0.8 mL/kg in a given 24-hour period; 2.4 mL/kg in a given 4-week period). Collection kits that limit blood volume draws are being used for pediatric participants. Investigators are allowed to limit blood sample collection in consideration of patient condition, with the guidance of a sample priority list (Table 10). Blood volume limits are following guidelines included in EU guidance for ethical considerations for clinical trials conducted with minors. Best practices for pediatric blood collection are provided in Section 9.3.3.1.
Potential DDI	Based on preliminary in vitro data, osivelotor has the potential to interact with CCI [REDACTED]	Close monitoring of the Prohibited/Restricted medication list

Adult participants in this study who have completed Part A of C5351004 (with open label osivelotor treatment), or any other open label osivelotor study, will be assessed every 12 weeks for safety and response to treatment.

Participants from Part B of C5351004, or any other randomized, blinded, placebo controlled osivelotor study, will be assessed every 8 weeks, for safety and response for the initial 24 weeks and then every 12 weeks thereafter.

Pediatric participants from Part C of C5351004 will be assessed at Week 2 and Week 4, then every 4 weeks for the initial 24 weeks, and then every 12 weeks thereafter.

For participants who have been off study drug treatment prior to enrolling into this study, an appropriate loading dose regimen will be initiated (Table 14), and participants will be assessed every 2 weeks up to Week 8, then every 4 weeks up to Week 24, and every 12 weeks thereafter.

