**Adult Participants from Part A of C5351004 and Other Applicable Osivelotor Open Label Studies with no Delay of Start**

**Table 2. Schedule of Assessments for Adult Participants from Part A of C5351004 and Other Applicable Osivelotor Open Label Studies with no Delay of Start**

	Treatment Period				
Study Week	Baseline visit	12	24	Every 12 weeks	EOS k /ET
Study Day	1 (± 30)	84 (± 7)	168 (± 7)	252+ (± 14 Days)	
Informed consent/assent	X				
Eligibility assessment	X				
Medical history	X				
Physical examination a	X	X	X	X	X
Height	X				
Weight	X	X	X	X	X
Vital signs b	X	X	X	X	X
Serology (hepatitis A, B, C, HIV) only if clinically indicated	X				
Hematology including reticulocyte count and serum chemistry		X	X	X	X
aPTT, INR, PT	X				
Serum erythropoietin	X	X	X	X	X
eGFR (for adults, children or infants) or eCrCl (adolescents) c	X		X	X	X
Urinalysis	X	X	X	X	X
Pregnancy test (for females, post menarche) d	X	X	X	X	X
Contraception check i	X	X	X	X	X

**Table 2. Schedule of Assessments for Adult Participants from Part A of C5351004 and Other Applicable Osiveltor Open Label Studies with no Delay of Start**

	Treatment Period				
Study Week	Baseline visit	12	24	Every 12 weeks	EOS k /ET
Study Day	1 (± 30)	84 (± 7)	168 (± 7)	252+ (± 14 Days)	
PK samples (whole blood and plasma) e	X	X	X	X	X
RBC deformability and RBC mitochondrial content (at sites where available) f,j	X	X	X	X	X
Flow adhesion f,j	X	X	X	X	X
Peripheral blood smear f,j	X	X	X	X	X
Exploratory Biomarkers 	X	X	X	X	X
PGI-C/CGI-C f	X	X	X	X	X
PGI-S/CGI-S f	X	X	X	X	X
PROMIS SF Fatigue 13a, SF Pain Interference 8a, and NRS Pain Intensity f	X	X	X	X	X
EQ-5D-5L f	X	X	X	X	X
WPAI+CIQ:SCD f	X	X	X	X	X
Qualitative interview f,g	X				
Study drug administration	←-----→				
Dispense study drug	X	X	X	X	
Return unused study drug h		X	X	X	X
Concomitant medication	X	X	X	X	X
Serious and nonserious AE monitoring	X	X	X	X	X

**Table 2. Schedule of Assessments for Adult Participants from Part A of C5351004 and Other Applicable Osiveltor Open Label Studies with no Delay of Start**

	Treatment Period				
Study Week	Baseline visit	12	24	Every 12 weeks	EOS k /ET
Study Day	1 (± 30)	84 (± 7)	168 (± 7)	252+ (± 14 Days)	

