## 5.3. Justification for Dose

The daily maintenance dose for adults in the open label extension study will be 150 mg, which was the optimal efficacious dose determined from Part A of C5351004. The daily maintenance dose for all adult participants who have already enrolled in C5351005 prior to this amendment may be adjusted to 150 mg.

Adolescent and pediatric participants from C5351004 Parts B and C will be administered a dose that provides generally equivalent exposure to adult participants.

Further modifications to the loading doses may be made based on cumulative data from a population PK (PPK) model. Additionally, if there are safety/tolerability issues or lack of biomarker response at higher doses in the originating study, a drug dose reduction may be instituted as noted in Section 11.3.

The methodology for loading dose selection used in this open label study will differ for participants completing Parts A, B, and C of C5351004 and are shown in Section 11.3 and Table 6. For participants from the parent study who have been off study drug treatment greater than 3 consecutive days prior to enrolling into this study, a new loading dose regimen will be initiated as shown in Section 11.3.

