### 6.1. Inclusion Criteria

Participants must meet all inclusion criteria to be eligible for study participation.

1. Aged 6 months or older with SCD who participated and received study drug in an osivelotor clinical study and completed the EOT visit.

Note: Participants who discontinued study drug in the originating study due to an AE, but who remained on study, may be eligible for treatment in this study provided the AE does not pose a risk for treatment with osivelotor. Also, participants who completed treatment from the originating study but were not able to rollover into C5351005 due to delay in study site activation will be eligible provided other eligibility criteria are met.

2. Females of child-bearing potential are required to have a negative urine pregnancy test prior to dosing on Day 1.

Note: Females who become of child-bearing potential during the study must be willing to have a negative urine pregnancy test to remain in the study.

3. If sexually active, females of child-bearing potential must consistently use highly effective methods of contraception consistently throughout the study and for at least 84 days after the last dose of study drug. Male participants are eligible to participate if they agree to the following requirements during the study intervention period and for 84 days after the last dose of study intervention, which corresponds to the time needed to eliminate reproductive safety risk of the study intervention:

- Refrain from donating sperm

PLUS either:

- Be abstinent from heterosexual intercourse as their preferred and usual lifestyle (abstinent on a long-term and persistent basis) and agree to remain abstinent.

OR

- Must agree to use a male condom when engaging in any activity that allows for passage of ejaculate to another person.

A male participant should be advised of the benefit for a female of child-bearing potential partner using a highly effective method of contraception with a failure rate of <1% per year.

4. Has provided written informed consent/assent. For underage participants, both the consent of the participant's legal representative or legal guardian and the participant's assent (where applicable) must be obtained based on local requirements.

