**Table 7. Study Drug Information**

Study Intervention	
Intervention Name	Osivelotor (PF-07940367 or GBT021601)
Type	Drug
Use	Experimental
IMP or NIMP/AxMP	IMP
Dose Formulation	Tablet (or age appropriate oral formulation for pediatric participants <6 years of age)
Unit Dose Strength(s)	100 mg/tablet, 25 mg/tablet
Dosage Level(s)	100 mg, 150 mg, 200 mg
Route of Administration	oral
Sourcing	Provided centrally by the sponsor.
Packaging and Labeling	Study intervention will be provided in bottles. Each bottle will be labeled as required per country requirement. Provided blinded.
SRSD	PF-07940367 Investigator's Brochure
Study Arms	
Arm Title	Osivelotor (PF-07940367 or GBT021601)
Adults	Adult participants enrolling from C5351004 Part A and Part B will receive 150 mg maintenance dose. Dose adjustment and/or loading dose will be determined based on previous intervention/dose received in C5351004. Details are provided in Appendix 1.
Adolescents and Pediatrics	Adolescent and pediatric participants from C5351004 Parts B and C will be administered a dose that provides generally equivalent exposure to adult participants.

See [Appendix 1: Detailed Dosing Information For Osivelotor](#) for dose information for participants rolling into this study.

Osivelotor will be administered orally. Study drug will be dispensed to the participant for completion of loading doses and initiation of maintenance dosing at home daily until the next clinical site visit.

Study drug should be taken two hours before a meal or one hour after a meal. Each dose will be administered orally with approximately 240 mL of water (additional water to complete dosing is allowed). Participants should swallow the tablets ( $\geq 6$  years old) or age appropriate

pediatric formulation (<6 years old) within 5 minutes. If the participant vomits, the dose should not be repeated.

On the days that PK samples are to be taken, study drug is to be taken in the clinic and the participant must record the time and date of the last three doses of study drug taken at home. It is anticipated that these samples are to be taken  $24 \pm 3$  hours after the last dose at home.

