Instructions for recording VOC events and source document collection for VOC event adjudication are provided in Section 9.4.12.1.

For participants with a gap in dosing >42 consecutive days from completing the originating study, outcome measures will be evaluated at the end of the loading dose period (Week 1), then every 2 weeks for the first 2 months (up to Week 8), then every 4 weeks for 4 months (up to Week 24), then every 12 weeks thereafter.

For participants from Part A of C5351004 or any other open label osivelotor study, outcome measures will be evaluated every 12 weeks.

For participants from Part B of C5351004, or any other randomized, blinded, placebo controlled osivelotor study, outcome measures will be evaluated every 8 weeks for the first 24 weeks of treatment in the open label study, and every 12 weeks thereafter.

For pediatric participants from Part C of C5351004, outcome measures will be evaluated at Week 2 and Week 4, then every 4 weeks for the first 24 weeks of treatment, and then every 12 weeks thereafter.

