**Table 14. Modified Loading Dose for Those with a Gap in Treatment from C5351004 Part A, Part B, and Part C**

Amount of Consecutive Days with Missed Doses	100 mg Maintenance Dose	150 mg Maintenance Dose	200 mg Maintenance Dose
>3 to <7 consecutive days of missed doses	200 mg QD x 3 days	300 mg QD x 3 days	300 mg QD x 4 days
7 to <14 consecutive days of missed doses	200 mg QD x 5 days	300 mg QD x 5 days	300 mg QD x 7 days
14 to <42 consecutive days of missed doses	200 mg QD x 7 days	300 mg QD x 7 days	300 mg QD x 10 days
42 consecutive days of missed doses or greater	200 mg QD x 7 days	300 mg QD x 7 days	300 mg QD x 14 days

Abbreviations: BID, twice daily; QD, once daily.

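### Part A adults re-loaded after 4 to 42 days off drug have no scheduled visit before Week 12, and the SAP pools their largely off-drug baselines with on-drug ones

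*Protocol*

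**What the plan says.** **Re-loading.** Protocol Section 5.3 sets the trigger: for parent-study participants "off study drug treatment greater than 3 consecutive days prior to enrolling into this study, a new loading dose regimen will be initiated". Table 14 grades the load by gap, and one tier is "14 to <42 consecutive days of missed doses". Section 7.1 provides for "completion of loading doses and initiation of maintenance dosing at home daily". Gaps were foreseen: inclusion criterion 1 admits people who finished the originating study but "were not able to rollover into C5351005 due to delay in study site activation".

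**Monitoring.** Section 3.2.1 says of participants off drug before entry that "an appropriate loading dose regimen will be initiated (Table 14), and participants will be assessed every 2 weeks up to Week 8", and states no minimum gap. Section 9.2 restricts early visits: "For participants with a gap in dosing >42 consecutive days from completing the originating study", assessments fall at Week 1, then every 2 weeks to Week 8. It then says: "For participants from Part A of C5351004 or any other open label osivelotor study, outcome measures will be evaluated every 12 weeks". Protocol Table 1 carries the same limit of more than 42 days. Protocol Table 2, titled for "Osivelotor Open Label Studies with no Delay of Start", has Week 12 as its first visit after baseline.

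**Analysis.** SAP Section 2.2.3 says only Part A adults entered. It splits them at a gap of 42 days (first OLE dose minus parent EOT date, plus 1), each set on its own schedule. SAP Section 5.3 uses the same split for its columns, and Section 6.4 plans no subset analyses. SAP Appendix 1.2 takes baseline from the parent Week 12 visit if the gap is under 7 days, and from pre-dose OLE Day 1 otherwise. SAP Table 5, for the group without delayed start, opens its first post-baseline window at Day 42.

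**The concern.** The protocol uses one threshold for re-loading (more than 3 days) and another for early monitoring (more than 42 days). Section 3.2.1 reads as if they were the same. Adults between the two restart on a loading regimen with no scheduled check for about 12 weeks.

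The SAP carries the 42-day line into its columns, so re-loaded adults sit with adults who never stopped. Safety is the primary objective, labs and vital signs are primary endpoints, and hemoglobin change is secondary. The delayed-start split is the only planned view of what happens on restarting, and it omits these adults. The other column is meant to describe continued dosing, but its changes from baseline mix two quantities: maintenance from an on-drug level, and recovery from an off-drug level.

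**Working it through.** **1. Scheduled visits between baseline and Week 12** (counted from Protocol Section 2.1)

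| | Protocol Table 1 (gap >42 days) | Section 3.2.1 text | Protocol Table 2 |
|---|---|---|---|
| Visits | 5 (Weeks 1, 2, 4, 6, 8) | 4 (Weeks 2, 4, 6, 8) | 0 |
| Vital signs, AE check | 5 | not itemised | 0 |
| Hematology and chemistry | 4 | not itemised | 0 |
| PK | 2 (Weeks 4, 8) | not itemised | 0 |
| Erythropoietin | 0 | not itemised | 0 |

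**2. Loads compared** (Protocol Table 14)

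- 100 mg: 200 mg daily for 7 days, for both 14 to <42 days and 42 days or more.
- 150 mg: 300 mg daily for 7 days, for both.
- 200 mg: 300 mg daily for 10 days against 14 days.

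After a 7-day load, the first Table 2 visit (Day 84 ± 7, so Days 77 to 91) comes 77 − 7 = 70 to 91 − 7 = 84 days later.

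**3. Which baseline applies.** If the EOT date is the last dose date, the SAP gap equals missed days + 2. Four missed days give a gap of 6 (parent Week 12 baseline, on drug). Five or more give 7 or above (OLE Day 1 baseline). The 42-day limit corresponds to 40 missed days on that reading, so the upper edge is approximate.

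**4. How far off drug the Day 1 baseline is.** Protocol Section 3.1 gives a half-life of about 10 days in SCD. Fraction remaining t days after the last dose = 0.5^(t/10). The brackets use assumed half-lives of 7 to 14 days.

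- t = 6: 66% (55–74%)
- t = 14: 38% (25–50%)
- t = 28: 14% (6–25%)
- t = 41: 6% (2–13%)

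**5. Illustration for hemoglobin.** Assumptions: the on-drug gain is 2.3 g/dL (the mean in six adults, Protocol Section 3.1), and hemoglobin falls in proportion to drug lost, or by half of that if it lags. Hemoglobin regained on re-treatment, at a 10-day half-life:

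- t = 14: 2.3 × (1 − 0.379) = 1.43, halved 0.71 g/dL
- t = 41: 2.3 × (1 − 0.058) = 2.17, halved 1.08 g/dL

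The shift in the pooled mean change is the share of such adults times the amount regained. The shares are assumed:

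- 10%: 0.07 to 0.22 g/dL
- 25%: 0.18 to 0.54 g/dL
- 50%: 0.36 to 1.08 g/dL

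**6. Windows.** SAP Table 5 leaves Days 2 to 41 (40 days) without a window. Protocol Table 2 schedules no visit on those days, so only unscheduled results are affected.

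**The case against.** The strongest reply is that Section 3.2.1 also puts Part A adults on 12-weekly visits, and that its 2-weekly sentence is shorthand for the group with gaps above 42 days, whose timetable in Section 9.2 is nearly the same. Section 9 makes the schedule of assessments binding, and SAP Section 2.2.3 confirms two sets on two schedules. Sites would therefore follow Table 2. This is a fair account of what probably happened. It does not rescue the text, which refers to Table 14 and so to every gap above 3 days. It also leaves the pooling untouched.

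It can also be said that the 42-day line separates essentially washed-out participants, that the SAP states its column definition openly, that investigators may order extra safety labs, and that all summaries are descriptive. All of that is true. But a 28-day gap already leaves only about 14% of drug, and no planned table shows those adults apart.

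Four stronger readings are tempting, and the documents do not support them:

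- **Adverse events during re-loading are lost.** They are recorded from consent and count as TEAEs from the first dose.
- **The SAP discards scheduled early data.** SAP Table 5 fits the Protocol Table 2 schedule. A loss of planned visits would require a site to depart from that schedule.
- **Two baseline rules compete.** The SAP Table 5 footnote is incomplete, but it refers to Appendix 1.2, which settles the matter.
- **This group alone lacks early erythropoietin.** Protocol Table 1 has none between baseline and Week 12 either.

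**Conclusion.** The point holds. Section 3.2.1 describes early monitoring that the schedule does not give to Part A adults re-loaded after shorter gaps: 0 visits before Week 12, against 4 in that text and 5 in Protocol Table 1. For gaps of 14 to under 42 days at 100 or 150 mg, the load is identical to that of the monitored group. Followed as written, the SAP averages on-drug and off-drug baselines in one column, so mean changes there are partly re-treatment effects.

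The visit counts and the mixing of baselines follow from the text alone. The size of the shift does not. A reader might take the hemoglobin figures as an estimate of bias, but the shares are assumed, the 2.3 g/dL comes from six adults in another study, and the number of affected adults is not reported and could be zero. The point is worth settling before the analysis, but it does not threaten the capture of adverse events.

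**What to change.** In the SAP:

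- (a) Report how many participants had gaps of 3 days or less, 4 to 42 days, and more than 42 days, stating whether the bands count missed doses or use the SAP formula.
- (b) Present TEAEs, labs, vital signs and hemoglobin change for re-loaded adults with gaps of 4 to 42 days separately from uninterrupted adults, or in a listing if there are very few.
- (c) Amend the SAP Table 5 footnote to say that Appendix 1.2 rule 2 applies when the gap is 7 days or more. List unscheduled labs and vital signs from Days 2 to 41. Do not re-window them: such tests may be done for cause, and their presence should not decide the analysis visit.

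In the protocol:

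- (d) If entry is still open, apply Protocol Table 1 to every gap that triggers a loading dose. If it is closed, as SAP Section 2.2.3 suggests, correct Section 3.2.1 and state in the study report that these adults had no scheduled visit between baseline and Week 12.

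The SAP cost is one flag from two dates already in its Section 5.3 formula, plus one extra set of columns or a listing, possibly sparse. If no participant had a gap of 4 to 42 days, only the text corrections remain.

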### 3.2.2. Benefit Assessment

Osivelotor increases hemoglobin (Hb) oxygen affinity and stabilizes Hb in the oxy-hemoglobin state thereby inhibiting polymerization of HbS in RBCs and increasing RBC deformability and reducing morphologic sickling of RBCs (Dufu, Alt et al. 2020). In preclinical animal studies, osivelotor partitioned preferentially to the RBC compartment with a mean blood/plasma ratio of 48–122:1. Thus, similar to voxelotor, osivelotor is expected to

partition preferentially into RBCs in humans, where it specifically binds to Hb, thereby minimizing plasma exposures.

- SCD is a serious condition characterized by hemolytic anemia, chronic organ damage, and VOCs. Despite recent advances in therapy, there remain limited treatment options for patients with SCD; thus a high unmet medical need continues to exist. Osivelotor's potential to address this unmet medical need is supported by the nonclinical studies and preliminary clinical data which provide evidence for a treatment effect (gradual increase in Hb at both 100 mg and 150 mg daily maintenance dosing in C5351004). Given the MOA, it is likely that higher Hb levels (and consequently a clinically significant reduction in the incidence of VOCs) will be achieved, which is supported by data for Hb and Hb occupancy from C5351002 and preliminary data for C5351004.
- Osivelotor has increased affinity for Hb and a longer  $t_{1/2}$  compared to voxelotor. Osivelotor has the potential to achieve greater % Hb occupancy and attain desired hematological effects at lower doses than voxelotor, therefore reducing pill burden, increasing the durability of response, and improving clinical outcomes for individuals living with SCD.
- The current treatment options for pediatric participants with SCD, particularly in children less than 12 years of age, are limited. SCD requires life-long preventive maintenance and management of acute and chronic complications. Newborn screening, early immunization, and prophylactic penicillin treatment in infants and children as well as comprehensive management for pain and disease complications have improved outcomes in children with SCD. Despite these advances, the median life expectancy of affected individuals is only 43 years of age and treatment of SCD remains a serious unmet medical need ([Brandow, 2022](#)). C5351004 Part B will evaluate the efficacy and safety of the selected dose of osivelotor versus placebo in adult and pediatric participants (12 to <18 years of age) with SCD. Part C will evaluate the PK and safety of single and multiple doses of open-label osivelotor administered to pediatric participants 6 months to <18 years of age.

